6. BASELINE SURVEY

Each physician's office will be provided with simple case report forms (questionnaires) for collecting data at baseline. The baseline visit will take place at the participating physician's office. All women who receive a new prescription for an oral contraceptive are to be asked if they are willing to participate. Only after the OC has been prescribed will the physician discuss the study with the subject. This ensures that participation in the study is not considered a requirement for treatment. After discussing the study details (including follow-up procedures and intervals, content and duration of follow-up contacts, use of data collected, etc.), each subject will be asked to provide written informed consent to participate in the study. If the subject needs time to consider participation, she will be permitted to leave the

physician's office with her prescription and take an appropriate period to decide whether to participate.

The informed consent will include permission for study data to be collected and analyzed and for contacts to be made by the study team at intervals during the follow-up phase for collection of study information. Each subject will also be asked to provide information regarding alternative contacts (a close relative or friend, or primary care physician) if the study team cannot reach the subject after several attempts. Permission for the study team to contact a subject's primary care physician/ attending physician(s) and to review relevant source data (e.g., medical reports for validation of reported serious clinical outcomes) will also be sought. Follow-up frequency by the study team will be explained, and the content of follow-up contacts will be described.

Confidentiality will be maintained throughout the study and no personal information will be shared with alternative contacts. The funder - Bayer Schering Pharma AG - will not have access to names, addresses, or alternative contact information for the subjects and all individual subject data will remain anonymous. Personal and medical information will be recorded on separate documents. ZEG will ensure that access to personal information is restricted in accordance with data privacy rules.

Baseline data will be recorded on a self-administered questionnaire containing queries relating to the participant's state of health and potential risk factors. Demographic data, medical and gynecological history, medication history (incl. vitamins) and history of OC use, family history of cardiovascular, colorectal and breast cancer related outcomes, reasons for OC use, as well as the addresses, e-mail addresses and phone numbers of the patient, relatives or friends, and the primary care physician are to be provided. In compliance with data protection regulations names, addresses and phone numbers are to be documented on a separate sheet.

7. FOLLOW-UP

A follow-up assessment for each woman is scheduled 6, 12, 18, 24 months after baseline, and then 3, 4, 5, 7½, 10, 12½, 15 years after recruitment. Women will be followed-up for at least 12 years. Women recruited in the early phase of the study will be followed-up until study endpoint [max. 15 years]. During Part II of the study (cf. Section 12) women will be followed-up at 2 ½ yearly intervals. Based on investigator experience from other long-term studies, women who remain in the study for 5 years are likely to remain in the study, even if follow-up periods extend beyond one year.

Follow-up questionnaires will be mailed to the participating women, who often know more about their own personal health related issues than the physician who prescribes their OC. This is especially true for potential adverse events treated by other

physicians. Occasionally, events may be reported by the participant or by a participant's relatives, friends or attending physicians between the regular follow-ups. These reports will be documented and validated in the same way as regular reports (see section 8).

In addition to the follow-up questionnaires, at the 18-month follow-up, a validated food-frequency questionnaire (Dietary Folate Equivalents (DFE) screener) specific for folate intake will be sent to study participants. Folate intake has a relatively stable intra-person variability, particularly in individuals consuming a western diet. In contrast, inter-person variability tends to vary significantly. A single DFE screener during the follow-up period will rank individuals in regard to their average dietary folate intake (inter-person variability) and provide sufficient information for analysis purposes. The DFE is a validated and widely used methodology for capturing micronutrient data in large populations and can be tailored for individual countries. It is expected that women use OCs for an average of approx. 3 to 4 years. Follow-up at 18 months would therefore be a good predictor of folate intake during OC use.

A low "lost to follow-up rate" will be essential for the validity of the study. In order to minimize loss to follow-up a multi-faceted, four-level follow-up process will be established. Level 1 activities include mailing of the follow-up questionnaire and – in case of no response – reminder letter(s). If level 1 activities do not lead to a response, multiple attempts are to be made to contact the woman, friends, relatives and the gynecologist/primary care physician per phone. In parallel to these level 2 activities searches in national and international telephone and e-mail address directories are started (level 3 activities). If this is not successful, an official address search via the respective governmental administration will be conducted. This level 4 activity can provide information on new addresses (or emigration or death). If necessary, a search in the national death registers could be started at the end of the study to clarify the vital status of patients who are lost to follow-up after level 4 activities. Specific follow-up procedures will be governed by local peculiarities. Overall, the loss to follow-up of the combined cohort should be kept at less than 5% and 10% of the recruited population for Europe and the US, respectively.

The follow-up questionnaires will address the occurrence of adverse events. Reasons for switching to another OC or discontinuation will be requested if applicable. In case the use of COC+ or other OCs was discontinued due to the wish to conceive, or due to intended or unintended pregnancy, a follow-up questionnaire requesting data on pregnancy related outcomes (abortions, stillbirths and congenital abnormalities) will be sent to the study participant.

8. VALIDATION OF SELF-REPORTED EVENTS

A self-administered questionnaire used by study participants is a very sensitive tool which captures almost all serious clinical outcomes. From a methodological point of view, it captures a much higher proportion of these outcomes than methods relying only on the prescribing gynecologist who often is not involved in the diagnosis and treatment of these outcomes. However, it must be considered that there is a significant difference between the rates of reported and validated events, because laypersons often misclassify adverse events. Therefore, validation of the self-reported events is of utmost importance.

Validation of self-reported events begins at the level of the national field organization with a review of all subjective "events." Potential serious outcomes are reported to ZEG on a daily basis and validated by ZEG.

If an event is reported by a participant, the subjectively perceived symptoms, signs of a disease and if possible the diagnosis as understood by the patient has to be recorded. The name and address of the relevant physician (attending physician, physician responsible for the follow-up treatment after discharge from hospital, or primary care physician) should be provided by the participant.

Follow-up questionnaires containing information on such an event are to be immediately passed on to the medical reviewer group at ZEG. If information is unclear or missing the woman will be contacted by phone, e-mail or other means. For many serious outcomes it will be necessary to contact the diagnosing and/or treating physician for clarification and validation of the information received from the patient. This procedure is mandatory for all serious clinical outcomes (incl. VTE, ATE and cancer).

Under routine medical conditions, diagnosis of an SAE is not always confirmed by a diagnostic method with high specificity. Therefore, SAEs are classified by the investigators as "confirmed" or "not confirmed" according to a predefined algorithm (cf. Appendix 1).

In order to minimize classification bias - particularly if selectively affecting an individual exposure cohort - classification of self-reported serious events into confirmed and not confirmed cases will be adjudicated by two blinded medical boards. The 'Cardiovascular Board' consists of three independent medical experts specialized in radiology/nuclear medicine, cardiology, and internal medicine/phlebology. The meetings of this board should take place 5 years after study start. The 'Colorectal Cancer Board' consists of an oncologist specialized in colorectal cancer, a pathologist and a radiologist. Blinded adjudication of CRC are scheduled for 5 years after study start and at the end of the follow-up phase (15 years after study start). The Safety Monitoring and Advisory Council (see section 13) will appoint these experts who will review all available information on the reported VTE/ATE/CRC.

However, brand names, dose, regimen and composition of the OC(s) used by the reporting woman will be rendered anonymous. The adjudicators will perform the review independently of each other and without knowing the judgement of the other adjudicators. If at least one adjudicator classifies a report as confirmed VTE or colorectal cancer, the reported event will be considered 'confirmed'. More details on the blinded adjudication procedure are given in Appendix 2.

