3. STUDY DESIGN

This is a large, transatlantic, prospective, controlled, non-interventional, long-term cohort study which follows three cohorts, users of DRSP/EE+², DNG/EE+ and users of OCs containing other estrogen/progestogen combinations. The users will be grouped to 'starters' (first-ever users) 'recurrent users with a break' (re-starters and switchers with a pill intake break) and 'recurrent users without a break'. 'A break' is defined as cessation of OC intake of at least one treatment cycle. A "non-interference" approach³ will be used to provide standardized, comprehensive, reliable information on these groups of OCs under routine medical conditions. In this study, regular, active contacts with the cohort members (active surveillance) should provide all necessary information on health-related events or changes in health status during new OC use.

There will be active contacts with all study participants at baseline, every six months for the first two years, annually from years 3-5 and thereafter every 2½ years (total of

² e.g., 21-day regimen of 3mg DRSP/30µg EE and 24-day regimen of 3mg DRSP/ 20µg EE containing metafolin

³ i.e., 1) all patients who are new users of an OC - regardless of the type of estrogen or progestogen - are eligible for enrollment if they give their informed consent and 2) the recruitment of patients should not (significantly) influence the physician's prescribing behavior.

11 follow-up questionnaires)⁴. By means of these contacts, almost all relevant clinical outcomes will be captured. However, laypersons often misclassify adverse events (e.g., pain in the legs after standing a long period of time as “thrombosis” or migraine attacks as “stroke” even if modern imaging procedures do not provide any indication of the perceived event). This type of inaccuracy in patient reports requires careful validation of the reported events. This will be accomplished by contacting the relevant physicians and by reviewing relevant source documents. Under routine medical conditions, diagnosis of a VTE is not always confirmed by medical imaging. A standard algorithm will be used to classify VTE cases as “confirmed” or “not confirmed”. For cancer endpoints, a disease-specific algorithm incorporating histological diagnosis will be used (cf. section 8 and Appendix 1). At the end of the study this classification will be verified by blinded independent adjudication (cf. Appendix 2).

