9. REPORTING OF SERIOUS AND/OR UNEXPECTED ADVERSE EVENTS

ZEG will report all serious⁵ and/or unexpected events that are possibly related to the use of any OC to the relevant pharmaceutical companies. A physician on the ZEG study team will assess the likelihood of a causal relationship to OC use for each serious adverse event in accordance with a predefined algorithm (cf. Appendix 3). Overall, the handling of adverse events will follow Volume 9A of 'The Rules Governing Medicinal Products in the European Union (part I, section 7).

ZEG will not monitor whether these companies meet their obligation to report these events to the Health Authorities according to (inter)national rules.

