A detailed statistical analysis plan will be developed by the Principal Investigator during the first year after study start. The final analysis plan will be approved by the Safety Monitoring and Advisory Council before the first interim analysis of follow-up data.

Within the first 5 years biannual interim reports will be provided to the funder following release of the interim analyses results by the independent Safety Monitoring and Advisory Council (cf. section 13). In the following years annual reports will be provided.

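### The investigators' own verdict and causality code are not among the items withheld from the blinded boards, which leaves an anchoring route open

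*Protocol*

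**What the plan says.** **First classification.** Under section 8, "SAEs are classified by the investigators as" confirmed or not confirmed, following the Appendix 1 algorithm. No masking is stated for this step. On incoming material the section says: "Follow-up questionnaires containing information on such an event are to be immediately passed on to the medical reviewer group at ZEG". Section 7 says of the same questionnaires: "Reasons for switching to another OC or discontinuation will be requested if applicable". Section 9 adds: "A physician on the ZEG study team will assess the likelihood of a causal relationship to OC use for each serious adverse event". ZEG also reports possibly related events to the company concerned.

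**Boards.** Section 8 gives the purpose of the two blinded boards as reducing classification bias, above all bias confined to one exposure cohort. Their members are experts "who will review all available information on the reported VTE/ATE/CRC". The masking rule follows: "However, brand names, dose, regimen and composition of the OC(s) used by the reporting woman will be rendered anonymous". Adjudicators work independently and do not see one another's judgements. Section 3 describes the step so: "At the end of the study this classification will be verified by blinded independent adjudication". Section 8 places the cardiovascular adjudication at 5 years after study start, and the colorectal adjudication at 5 and 15 years.

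**Use of the results.** Appendix 2 bases the final analysis on strategy III: an event counts if at least one adjudicator confirms it before any discussion. Section 11 states: "Within the first 5 years biannual interim reports will be provided to the funder".

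**The concern.** A board protects against cohort-dependent classification only if its judgement is independent of a judgement that may depend on cohort. Section 8 hides the product and the other adjudicators' votes. It does not hide the one earlier opinion that was probably formed with the product in view. An adjudicator with a doubtful report who can see that ZEG has already called it confirmed, or has coded it as probably related to the pill, may lean the same way. The wording of section 3, under which the boards verify an existing classification, encourages that.

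Doubtful cases will occur. Appendix 1 counts probable events as confirmed on low-specificity tests or a clinical diagnosis, and section 8 accepts that a highly specific test is not always available. The primary VTE hazard ratio, the ATE comparison and the colorectal cancer comparison all depend on these calls.

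There is also a smaller point on the interim reports. No board result exists before year 5, so any count of confirmed events before then can come only from ZEG.

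**Working it through.** **1. What is hidden from the boards, item by item**

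| Item | Withheld? | Source |
|---|---|---|
| Brand, dose, regimen, composition | Yes | Section 8 |
| Other adjudicators' judgements | Yes | Section 8 |
| ZEG confirmed/not confirmed verdict | Not stated | On neither list in section 8, nor in Appendix 2 |
| Appendix 3 causality code | Not stated | Same |

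**2. Does ZEG know the product?** The protocol never says so outright. The reviewer group receives the questionnaires, which cover switching and stopping; a ZEG physician judges causality to pill use; and reports go to the company concerned. Product knowledge within ZEG is therefore very likely, but it is an inference.

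**3. Interim reports affected.** Read as twice a year, which agrees with the six-monthly council meetings in section 17, five years give 5 × 2 = 10 reports, or 9 before the year-5 evaluation itself.

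**4. The plan's own figures.** Table 3 reproduces with n(ref) = (1.960 + 1.282)² × p(1 − p) × (1/k + 1) / margin², where p = margin = 0.0009 and k = share/(1 − share). The result is 12,542 and 166,635 WY at a 7% share, and 13,255 and 97,204 WY at 12%. Each is within 1 WY of the table.

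**5. Leverage of one case at year 5.** Section 12 expects 185,000 exposed WY at 9/10,000, that is 166.5 VTE.
- 7% share: 12,950 WY × 0.0009 = 11.7 product events and 154.8 reference events.
- 12% share: 22,200 WY × 0.0009 = 20.0 product events and 146.5 reference events.
- One case changed in the product cohort moves the crude ratio by 1/11.7 = 8.6% or 1/20.0 = 5.0%.
- One case changed in the reference cohort moves it by 1/154.8 = 0.6% or 1/146.5 = 0.7%.

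**6. Direction under strategy III**
- Following a confirmed verdict on a DRSP/EE+ report takes one adjudicator. It raises the hazard ratio and makes non-inferiority harder to show.
- Following a confirmed verdict on a reference report also takes one adjudicator and lowers the ratio. Many cases would be needed: a ratio factor of 0.9 requires 11% more reference events (1/0.9 = 1.11), about 17 at a 7% share or 16 at 12%.
- Following a not-confirmed verdict on a DRSP/EE+ report removes the case only if all three adjudicators reject it.

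**7. Illustration only.** Let s be the net confirmation ratio, DRSP/EE+ to reference. The values of s are assumed; the protocol gives none. The results come from 400,000 Poisson simulations of a Wald test of HR < 2 at the year-5 exposure.

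| Share | s | Declares non-inferiority, true HR 2 | Declares non-inferiority, true HR 1 |
|---|---|---|---|
| 7% | 1.0 | 1.9% | 68.4% |
| 7% | 1.1 | 0.6% | 56.5% |
| 7% | 0.9 | 5.0% | 79.1% |
| 12% | 1.0 | 2.1% | 89.0% |
| 12% | 1.1 | 0.6% | 79.5% |
| 12% | 0.9 | 7.0% | 94.9% |

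The simulation tests the ratio, whereas Table 3 works on the difference in incidence, so the last column is not comparable with the planned 90%.

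**The case against.** The main hazard is already dealt with. The final analysis rests on independent experts masked to product, who judge all reported events rather than only those ZEG confirmed, and it uses their votes before discussion. The sentence in section 3 is a short preview; section 8 and Appendix 2 set the procedure. The information sent to the boards may well mean clinical and source documents, and a board charter that is not shown may exclude ZEG's opinion. ZEG itself follows the Appendix 1 algorithm and must contact the treating physician for VTE, ATE and cancer, which limits discretion. The causality code grades timing, pharmacology and alternative causes. All participants enter as pill users, so it need not reveal the cohort. Nothing says that the physician who codes causality is the one who classifies.

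Most of this stands, and it limits the point to anchoring. It does not remove it: the protocol itself fixes the list of masked items, the verdict is not on it, and the stated purpose is to exclude exactly this kind of influence.

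A reader might go further and infer that the primary result is biased, or that the false non-inferiority rate is raised. The documents do not support either. No rate of doubtful cases or of differential confirmation is given, and a raised false non-inferiority rate needs net under-confirmation of DRSP/EE+ relative to the reference. The one-adjudicator rule works against losing DRSP/EE+ cases. A reader might also infer that ZEG reviewers must be masked. That would need rolling redaction and split roles in a group that has to contact women and their physicians, a debatable trade-off.

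**Conclusion.** The point holds in a limited form. The blinding in section 8 is incomplete against its own aim, because a verdict very likely formed with knowledge of the product, and the causality code, are not withheld from the boards. Bias can reach the final VTE, ATE and colorectal cancer analyses only through anchoring on what the boards are shown. That is possible, not demonstrated.

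Its size cannot be derived from the protocol. What can be said is that one altered case in a product cohort of about 12 to 20 VTE shifts the hazard ratio by about 5 to 9%. This assumes the section 12 incidence and exposure and the 7 to 12% share. The simulated rates only show sensitivity to an assumed s, in either direction.

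Interim results before year 5 have no board classification to rest on. Section 11 does not name the event set they use, but a confirmed-event analysis at that stage can use only ZEG's classification.

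**What to change.** 1. In section 8 and Appendix 2, add the ZEG confirmed/not confirmed classification and the Appendix 3 causality code to the items removed from the file sent to the boards.
2. State there that the boards classify every reported VTE, ATE and colorectal cancer de novo from source documents, and bring the verification wording in section 3 into line.
3. Label interim results before year 5 as based on investigator classification that is not stated to be masked.
4. At year 5, report agreement between the ZEG and board classifications by cohort. This shows whether the earlier classification leaned towards one cohort.

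Items 1 to 3 cost a few sentences and a small clerical step in a file that must be redacted anyway. Item 4 is one table from data already held. No extra reads are needed. Masking the ZEG reviewers is optional and is not part of this recommendation.

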9. REPORTING OF SERIOUS AND/OR UNEXPECTED ADVERSE EVENTS

ZEG will report all serious⁵ and/or unexpected events that are possibly related to the use of any OC to the relevant pharmaceutical companies. A physician on the ZEG study team will assess the likelihood of a causal relationship to OC use for each serious adverse event in accordance with a predefined algorithm (cf. Appendix 3). Overall, the handling of adverse events will follow Volume 9A of 'The Rules Governing Medicinal Products in the European Union (part I, section 7).

ZEG will not monitor whether these companies meet their obligation to report these events to the Health Authorities according to (inter)national rules.

10. DATA MANAGEMENT

When questionnaires are received from study participants, all pages are counted and the questionnaire is date-stamped. Questionnaires are to be checked for correct subject identification number, missing pages, legibility, and incomplete information on the questionnaires (cf. section 7 'Follow-Up'). Missing pages, illegible or missing information are requested from the study participants prior to data entry of the respective questionnaire.

Data are entered by double data entry via formatted entry screens designed to reflect the appearance of the questionnaire. Discrepancies between first and second data entry are identified by comparison of the two entry files within the statistical software SAS. The decision on the true entry is done by the responsible data manager at ZEG. This may require direct contact with the study participant who filled in the questionnaire. Corrections will be made to the questionnaire only after contact with the study participant or her treating physician (cf. section 8 'Validation of Self-Reported Events'). All corrections are dated and initialled by the data manager who received the relevant new information (e.g., via direct contact or by a copy of medical reports/documents). The incorrect CRF entry will be crossed out; however, it must

⁵ Serious adverse event means any adverse event that results in death, a life-threatening experience, inpatient hospitalization, persistent or significant disability/incapacity, or requires medical/surgical intervention to prevent one of said outcomes.

remain legible, and the correct entry will be placed next to it. The reason for any correction of medical data on the questionnaire must be documented.

Quality control of entered data will be supported by SAS plausibility programs which include range, coding, missing and date checks as well as cross-reference (consistency) checks between variables.

